While the shared psychological factors in chronic pain and PTSD have been identified, the shared neurobiology is yet to be known.

Neurobiological Factors that Impact both Chronic Pain and PTSD: A Working Model

The neuroactive steroids, allopregnanolone and its equipotent stereoisomer pregnanolone (together termed ALLO +PA) may serve as potential mediators of the pain-trauma interrelationship.²¹⁻²³ These stress buffering molecules have been found to regulate pain.²²⁻²³ In addition, synthesis of these hormones is regulated by sex steroids such that there are both gender and menstrual cycle phase-related differences in their levels and reactivity that may impact both pain and PTSD symptomatology.

Allopregnanolone & Pregnanolone (ALLO): The neuroactive steroid allopregnanolone ($3\alpha,5\alpha$ -tetrahydroprogesterone) and its equipotent enantiomer, pregnanolone ($3\alpha,5\beta$ tetrahydroprogesterone) (collectively termed ALLO) are among the most potent positive modulators of the effects of gamma-amino-butyric acid (GABA) at GABA_A receptors. ALLO exerts anxiolysis, as well as analgesia at both supra-spinal and spinal levels. For example, Charlet, Lasbennes, Darbon and Poisbeau²⁴ showed that intrathecal injection of ALLO (i.e., injection into the fluid bathing the spinal cord at rat vertebral level L5-6) potently increased mechanical- and thermal pain thresholds in naive animals, as well as in animals with experimentally-induced inflammation. Kavaliers and Wiebe²⁵ similarly showed that intracerebroventricular injection of ALLO increased the thermal pain threshold with more potency than progesterone, while the

GABA_A receptor inactive 3β enantiomer of ALLO was ineffective. In addition, the analgesic effects of ALLO were blocked by GABA_A receptor antagonists and naloxone (an opiate antagonist), indicating that they involved the interactive activation of GABA_A and opiate receptors.

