Design Overview: The proposed research will assess the effects of aerobic and anaerobic exercise on ALLO+PA levels and changes in pain sensitivity among male and female Veterans with trauma exposure, chronic musculoskeletal pain and varying degrees of PTSD symptom severity. A total sample size of 30 participants (15 male & 15 female), aged 18-60 years, will be studied. To control for menstrual cycle effects, the women will be tested during the early follicular phase of the menstrual cycle when estrogen levels are low, and levels of progesterone (the steroid precursor for ALLO+PA) are stable and comparable to those in men. However, we will not be excluding women who are perimenopausal/menopausal. These patients will be scheduled during the same timeline as the male participants.

Recruitment methods Fliers will be posted within the VA and advertisements in the community.

Participant Characteristics: Participants will be receiving care in the VA Boston Healthcare System (VABHS) or recruited from the community. Inclusion criteria for the proposed study will permit the recruitment of women as well as men from all ethnic and racial backgrounds who are at least 18 years of age, and able to speak and understand English. The patient population at the VABHS is 65% Caucasian, 15% African American, 10% Latino, and 10% Asian. We intend to sample a similar demographic population as that served by the VABHS and will oversample for minorities to ensure that enough are seen.

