Exclusion criteria: Participants will be excluded from participation in the study if they have a life threatening or acute physical illness (e.g., cancer), current schizophreniform illnesses, **bipolar disorder**, or active suicidal or homicidal ideation requiring clinical intervention. Individuals with current or past alcohol and/or substance dependence (less than three months from date of screening assessment) will be excluded. Women who are or are planning to become pregnant within the next six months will also be excluded. Individuals seeking pain treatment such as surgical interventions or who have a neuropathic origin to their pain will also be excluded. Participants with chronic pain concerns that cannot tolerate exercising in an upright bike and those who have had a clinical history of coronary artery disease or positive stress test, uncontrolled cardiac arrhythmia, moderate-to-severe aortic stenosis, severe arterial hypertension (systolic >200 mmHg, diastolic >110 mm Hg) and more than first degree atrioventricular block also will be excluded from participation. Finally, individuals taking medications for chronic psychiatric or medical illnesses will not be excluded as long as their medications and medication dosing are stable for two months prior to participation in the study and remain stable throughout the 12 week exercise training protocol and final exercise test. Common medications that will be acceptable include psychotropic medications, steroid contraceptives, and medication for high blood pressure, high cholesterol and diabetes.

****In addition, participants may be excluded from further participation in the study at any point if he/she is unable to provide reliable study data, for example, altering his/her urine sample (in which case he/she would not be paid for the session), providing misinformation during an interview, or misinforming study staff of conditions that may exclude him/her from the study.**

Psychological and Behavioral Measures:

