Screening Evaluation for Study Eligibility: If considered potentially eligible and interested, participants will be invited for an in-person screening session in which they will first complete the informed consent process, according to the guidelines established by the Institutional Review Board (IRB) at the VABHS. After providing informed consent, the subject will answer assessment questionnaires and receive a physical examination, laboratory blood tests, a urinalysis, a urine toxicology test for illicit drugs, and an EKG. In addition to the initial qualitative "yes/no" test for tobacco use, we will test participants' urine cotinine level using Nymox NicAlert semi-quantitative test strips. Cotinine is the principal metabolite of nicotine and has a longer half-life (18 hrs vs. 2 hrs), and thus can be reliably used to estimate daily intake of nicotine. Cotinine tests will detect any tobacco use for the past few days, and therefore will be sensitive enough to test for any recent tobacco use when participants present for exercise assessment sessions. Although we will not be excluding tobacco users from the study, any level of tobacco use can impact accurate measurement of the antistress and antinociceptive neurohormones under investigation, therefore it is imperative that we are able to capture the level of cotinine for the participants who smoke and verify the non-smoking status of participants who identify as non-smokers. Finally, women will receive a urine pregnancy test at all in person study visits. The physical screening will be performed by [name] or her medical fellows.

**** Parts of the physical examination, lab tests, or the EKG and psychiatric assessments may be repeated in order to clarify results, or to track or evaluate possible medical/psychiatric problems during the study. To do this, the participant may be asked to return for an extra visit for which he/she will be compensated.**

****If a month or more of time lapses between the screening session and the baseline cold pressor assessment sessions, we will repeat the CAPS-5 to re-determine PTSD status, prior to any study procedures with the exception of the urine testing. Regardless of the outcome of the assessment, the participant will be compensated for the full amount of the cold pressor session.**

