Aim 1 : Hypothesis one will be evaluated by conditional LGMs. The Intercept of the LGM will be centered on the self report data from the baseline CPX assessment (i.e., first Slope loading will be fixed to 0.0). The intermittent time point (midpoint self-report session) will be freely estimated and the final time point (i.e the self-report data from the 13 week MAX-EX test session) will have a corresponding Slope factor loading fixed to 1.0. Accordingly, the mean and variance of the Slope factor will convey the fixed (average) and random effects (individual differences) of change for the time interval of interest. The two study groups will be dummy coded (using chronic pain/PTSD as the reference condition in the initial models) and included as predictors in the LGM to account for individual differences in symptom reduction (i.e. pain intensity, pain tolerance and threshold, depression and PTSD symptoms) due to treatment assignment. The Intercept will be regressed onto the treatment covariates to examine any pre-exercise training differences among treatment conditions. Moreover, individual differences in pre-treatment functioning will be held constant by regressing the Slope onto the Intercept. Hypotheses 1 will be supported in part by the statistical significance of the study group (dummy code) > Slope paths. In fact, these paths reflect study group x Time interaction effects. The nature of these interaction effects in the LGMs will be characterized using the procedures described by Curran, Bauer, and Willoughby.⁷⁸ All outcome measures will be analyzed in this fashion.

Aims 2 & 3: At both exercise assessment time-points, change scores will be computed ALLO+PA and these will be correlated with pain tolerance and pain threshold scores using Pearson or Spearman correlations, as appropriate. For exploratory purposes, ALLO+PA will be used as predictor variables in a regression equation to predict pain outcome (tolerance, threshold and intensity).

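### Aim 3 correlates ALLO+PA change with cold pressor scores across men and women without a sex term, so a sex difference in both could pass for the hypothesised association

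*Combined protocol and SAP*

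**What the plan says.** Under Data Analyses, the paragraph on Aims 2 & 3 computes change scores for ALLO+PA at each exercise assessment and then relates them to the cold pressor tolerance and threshold scores "using Pearson or Spearman correlations, as appropriate". No covariate or stratum is named. The only model offered for Aim 3 is secondary: "For exploratory purposes, ALLO+PA will be used as predictor variables in a regression equation to predict pain outcome". It too lists no other predictor. The recruitment and human-subjects text mentions gender comparisons, but the analysis plan specifies none.

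The sample is mixed by design: "A total sample size of 30 participants (15 male & 15 female), aged 18-60 years, will be studied" (Design Overview). The working-model section of the background says of these steroids that "there are both gender and menstrual cycle phase-related differences in their levels and reactivity that may impact both pain and PTSD symptomatology". The paragraph on sex-specific factors adds that women's pain comes more often, is worse and lasts longer than men's.

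Two further influences on ALLO+PA are acknowledged. The screening section warns that "any level of tobacco use can impact accurate measurement of the antistress and antinociceptive neurohormones under investigation" and has cotinine measured for that reason. The exclusion criteria state: "Common medications that will be acceptable include psychotropic medications, steroid contraceptives". Neither reappears in the analysis plan.

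The plan does act at the design stage. Design Overview, Scheduling for Women and Limitations place menstruating women's tests in the early follicular phase, when progesterone is close to male levels. Perimenopausal and menopausal women follow the men's schedule.

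**The concern.** The Aim 3 correlation is taken between people. A factor that shifts both ALLO+PA change and the pain score will therefore contribute to it, even if the two are unrelated among men and unrelated among women. The protocol's own background puts sex forward as such a factor. If one sex has both the larger ALLO+PA response and the higher tolerance, the induced correlation is positive, which is the direction of Hypotheses 3a and 3b.

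Two things are at stake: whether a significant result can be read as support for the proposed mechanism, and what is passed on. Specific Objectives says these data will supply effect sizes for a future trial, so a correlation that partly reflects sex would go into its planning.

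**Working it through.** The plan gives no power or error figure for the Aim 3 correlation. Its one sample-size statement (25 participants, effect size .35, 90% power) is not tied to this test, and nothing below on error rates rests on it.

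**Inputs**
- Equal sexes, 30 recruited (Design Overview).
- Dropout 18-20% (Power and Sample Size Considerations): 30 × 0.80 = 24 and 30 × 0.82 = 24.6, so about 24 completers.
- Sex differences d1 (ALLO+PA change) and d2 (pain score), in within-sex SDs. These are assumptions, because the documents give no SDs.
- Within-sex correlation set to zero.

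**Induced correlation.** With half the sample in each sex,

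r = 0.25·d1·d2 / √[(1 + 0.25·d1²)(1 + 0.25·d2²)]

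- 0.5 and 0.5: 0.0625 / 1.0625 = .06
- 0.8 and 0.5: 0.10 / √(1.16 × 1.0625) = .09
- 0.8 and 0.8: 0.16 / 1.16 = .14
- 1.0 and 1.0: 0.25 / 1.25 = .20

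**False-positive rate.** Simulated two-sided 5% test of the pooled Pearson correlation (40,000 runs per setting; 100,000 for 0.8/0.5):

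| d1 / d2 | induced r | N=24 | N=30 |
|---|---|---|---|
| 0 / 0.8 | 0 | 4.9% | 5.0% |
| 0.5 / 0.5 | .06 | 6.0% | 6.1% |
| 0.8 / 0.5 | .09 | 7.0% | not run |
| 0.8 / 0.8 | .14 | 10.1% | 11.3% |
| 1.0 / 1.0 | .20 | 15.8% | 18.9% |

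A partial correlation given sex rejected in 4.8% to 5.2% of runs in the settings where it was computed (all rows except 0.8/0.5). Inflation therefore needs a difference on both variables, and becomes material at about 0.8 SD on each.

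**What the documents say about d1.** The pilot reports BMI-normalised ALLO change without SDs. In the Pain/PTSD group it was 2.45 in women and 2.44 in men, a difference of 0.01. In trauma controls it was 2.84 and 3.6, a difference of 0.76 with men higher. Neither can be put on an SD scale.

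**Cost of adjusting.** Fisher z power with 0, 1 and 3 covariates, for three true correlations: .35 (the stated effect size read as r), .51 (the same figure read as f², √(.35/1.35)), and .61 (the pilot correlation of ALLO change with post-exercise threshold).

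| true r | N=25 | N=30 |
|---|---|---|
| .35 | 40.3 / 38.8 / 35.7% | 47.6 / 46.2 / 43.3% |
| .51 | 75.0 / 73.0 / 68.7% | 83.1 / 81.7 / 78.5% |
| .61 | 91.4 / 90.1 / 87.1% | 95.8 / 95.1 / 93.5% |

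One covariate costs about 1 to 2 points; three cost about 2 to 6.

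**The case against.** The strongest reply is that the protocol already controls the main route. Early-follicular testing brings women's progesterone, the precursor of ALLO+PA, close to male levels. That stands for resting levels in menstruating women. It does not answer the stated sex difference in reactivity, and it does not cover perimenopausal or menopausal women or users of steroid contraceptives.

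Second, the nearest in-document data show almost no sex difference in ALLO change in the Pain/PTSD group. This also stands and limits the likely size. It does not settle the matter: there are no SDs, trauma controls did differ, and the inclusion criteria also appear to admit trauma-exposed participants without PTSD or chronic pain.

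Third, the link from sex to pain in the background concerns reported clinical pain, not cold pressor results. Hypotheses 3a and 3b also speak of changes in sensitivity and tolerance. If the pain variable is a change score, stable sex differences in tolerance cancel. The analysis paragraph says scores, so the text leaves this open; only a sex difference in the change itself would then matter.

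Fourth, if sex acts on pain through ALLO+PA, conditioning on sex discards some real variation. That is a reason to show the unadjusted estimate alongside, not to omit adjustment.

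A reader might also infer that tobacco and steroid contraceptives create a spurious association in the same way. The documents do not support that. They tie tobacco to the hormone measurement, and the case for contraceptives rests on ALLO+PA deriving from progesterone, but no section links either to pain. On this evidence both are sources of noise in ALLO+PA, which would tend to weaken the correlation.

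**Conclusion.** The concern holds in a limited form. The planned Aim 3 test has no sex term, although the protocol's own background relates sex both to ALLO+PA reactivity and to pain. If sex shifts both variables in the same direction, the two-sided error at 24 completers is about 6% to 16% for differences of 0.5 to 1.0 SD on both, about 7% at 0.8 and 0.5 SD, and about 5% if only one differs. These figures assume equal numbers by sex, normal data and no within-sex association; the SD differences are assumptions.

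It would go too far to say that the correlation will be spurious, or that the plan ignores sex. The pilot means in the Pain/PTSD group point to little difference, and the follicular scheduling is a real control. That the analysis pools the sexes is itself read from the absence of any sex-adjusted or by-sex version. The case for change is that the remedy is cheap and uses a variable already recorded.

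**What to change.** In the Aims 2 & 3 paragraph, make the Aim 3 analysis a partial correlation adjusted for sex, Pearson or rank. Report the unadjusted and by-sex estimates beside it, the latter as description given about 12 per sex. State whether the cold pressor variable is a score or a change.

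Add two sensitivity analyses: one that further adjusts for cotinine level, and one that excludes users of steroid contraceptives. Describe both as dealing with noise in ALLO+PA rather than with confounding.

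The cost is wording in the analysis plan and one degree of freedom for sex. Using three covariates together would lose about 2 to 6 power points at 25 to 30 participants. Sex and cotinine are already recorded, and contraceptive use should be available because medications must be stable throughout. Eligibility and study procedures need not change.
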